5.7. End of Study

The end of study is defined as the last patient last visit at the end of the long-term follow-up phase. This is the last timepoint for data collection. A patient is considered on study as long as the patient is still in long-term follow-up.

The sponsor has the right to terminate this study at any time. Reasons for terminating the study early may include, but are not limited to, the following:

- The incidence or severity of AEs in this or other studies indicates a potential health hazard to patients
- Overall patient enrollment is unsatisfactory
- Data recording is inaccurate or incomplete
- Evidence of no clinical benefit

The sponsor will notify each investigator if a decision is made to terminate the study. Should this be necessary, prematurely discontinued patients should be seen as soon as possible for an EOT Visit and Safety Follow-up Visit.

The investigators may be informed of additional procedures to be followed to ensure that adequate consideration is given to the protection of the patient's interests. The investigator will be responsible for informing IRBs/IECs of the early termination of the study.

The sponsor has the right to close a study center at any time. The decision will be notified to the center in advance. Reasons for closing a center may include but are not limited to the following:

- Excessively slow recruitment
- Poor protocol adherence
- Inaccurate or incomplete data recording

- Good Clinical Practice noncompliance
- Study activity is completed (ie, all patients have completed and all obligations have been fulfilled)]

6. STUDY TREATMENT

6.1. Study Drug

6.1.3. Dosage and Administration

Pamiparib capsules will be administered orally twice a day, once in the morning and once in the evening. The time difference between 2 consecutive doses should be approximately 8 to 12 hours.

Patients will be instructed to swallow the capsules whole, in rapid succession, with water. [REDACTED]

A dose of pamiparib should be skipped if it is not taken within 2 hours of the scheduled time. An extra dose of pamiparib should not be taken to make up for a missed dose. If vomiting occurs during the course of treatment, no re-dosing of the patient is allowed before the next scheduled dose.

6.1.4. Dose Hold and Modification

AEs should be assessed as best as possible regarding their relatedness to pamiparib. Patients should continue on study with follow-up as outlined in [Sections 5.5](#) and [5.6](#).

Investigators should make every effort to maintain dose intensity in patients. Dosing of pamiparib can be withheld for up to 28 days consecutively. Dose reductions are allowed in 20 mg per dose decrements. If drug is held \geq 28 days, the medical monitor must be contacted before permanent patient discontinuation from pamiparib.

Criteria for treatment modifications and suggested guidelines for the management of some toxicities related to pamiparib are summarized below. These general guidelines may be modified at the discretion of the investigator based on discussions with the medical monitor and the best clinical judgment at that time; any decisions should be documented. Any toxicities related to pamiparib should be managed according to standard medical practice.

A maximum of 2 dose reductions is allowed before the patient must be permanently withdrawn from pamiparib. Dose levels for pamiparib are summarized in [Table 3](#). Pamiparib will be dose modified as outlined in [Table 4](#). For prolonged hematologic toxicities, interrupt treatment and monitor blood counts weekly until recovery. If the levels have not recovered to NCI-CTCAE Grade 1 or less after 4 weeks, further investigations should be considered, including bone marrow analysis and blood sample for cytogenetics. If MDS or AML is confirmed, discontinue pamiparib.

Table 3: Dose Levels for Pamiparib

Dose Level	Pamiparib
1	60 mg orally twice a day
-1	40 mg orally twice a day
-2	20 mg orally twice a day

Pamiparib may be dose-reduced for a maximum of 2 dose reductions.

Table 4: Criteria for Modification of Pamiparib Dosing for Related Adverse Events

Toxicity		Recommended Dose Modification ^a
Hematologic		
Anemia (hemoglobin)		
Hgb < 9.0 g/dL		
 • First occurrence of Hgb < 9.0 g/dL: Hold pamiparib and treat as medically indicated to get Hgb to \geq 9 g/dL, and then ↓ pamiparib by 1 dose level to 40 mg BID
Grade 2 (Hgb <10 - 8 g/dL)	Hgb <10 - 9 g/dL	Continue dosing at current dose level and treat with appropriate supportive care as medically indicated
	Hgb <9 - 8 g/dL	
 • Subsequent occurrence following dose reduction for anemia: 
 ○ Continue pamiparib without interruption with appropriate supportive care based on clinical assessment OR ○ Hold pamiparib and treat as medically indicated to get Hgb to \geq 9 g/dL, then restart at reduced dose level OR ○ Hold pamiparib and treat as medically indicated to get Hgb to \geq 9 g/dL, then ↓ pamiparib by 1 additional dose level to 20 mg BID
Grade 3 (Hgb <8 g/dL)		
 • Subsequent occurrence following dose reduction for anemia: 
 ○ Continue pamiparib without interruption with appropriate supportive care based on clinical assessment OR ○ Hold pamiparib and treat as medically indicated to get Hgb to \geq 9 g/dL, then restart at reduced dose level OR ○ Hold pamiparib and treat as medically indicated to get Hgb to \geq 9 g/dL, then ↓ pamiparib by 1 additional dose level to 20 mg BID
Grade 4 (life-threatening consequences; urgent intervention indicated)		
 • Second occurrence following dose reduction for anemia: 
 ○ Hold pamiparib and treat as medically indicated to get Hgb to \geq 9 g/dL, then ↓ pamiparib by 1 additional dose level to 20 mg BID • Third occurrence following 2 dose reductions for anemia: 
 ○ Discontinue pamiparib if anemia is not caused by any other confounding event, eg GI hemorrhage. ○ Hold pamiparib and treat as medically indicated to get Hgb to \geq 9 g/dL, then restart at reduced dose level.

Note:
 
 1) Weekly hematology test should be done for the first 3 cycles during the study. For all Grade 2 or higher anemia, hematology test should be done weekly thereafter until adequate recovery. 2) For any patients showing Hgb dropping $>$ 2 g/dL especially within a short time without alternative explanation such as gastrointestinal bleeding, ↓ pamiparib by 1 dose level should be considered. 3) Dose increase can be considered in certain cases, depending on approval from the medical monitor, provided Hgb has been maintained above 9 g/dL for at least 3 months 		

Toxicity	Recommended Dose Modification ^a
Neutropenia (absolute neutrophil count)	
Grade 3 (absolute neutrophil count < 1.0 - 0.5 x 10 ⁹ /L)	Hold pamiparib until resolved to ≤ Grade 2 or baseline 
 • If resolved ≤ 7 days, then maintain dose levels • If resolved > 7 days, then ↓ pamiparib by 1 dose level
Grade 4 (absolute neutrophil count < 0.5 x 10 ⁹ /L)	Hold pamiparib until resolved to ≤ Grade 1 or baseline and ↓ pamiparib by 1 dose level
Febrile neutropenia (absolute neutrophil count < 1.0 x 10 ⁹ /L with single temperature of > 38.3°C or sustained temperature of ≥ 38°C for > 1 hour)	Hold pamiparib until resolved and ↓ pamiparib by 1 dose level
Thrombocytopenia (platelet count)	
Grade 3 (platelet count < 50 - 25 x 10 ⁹ /L)	Hold pamiparib until resolved to ≤ Grade 1 or baseline and ↓ pamiparib by 1 dose level
Grade 4 (platelet count < 25 x 10 ⁹ /L)	Hold pamiparib until resolved to ≤ Grade 1 or baseline and ↓ pamiparib by 1 dose level
Renal	
Estimated glomerular filtration rate (CKD-EPI equation; Appendix 11)	
If ≥ 60 mL/min/1.73 m ² at baseline: < 30 to 15 mL/min/1.73 m ² or If < 60 mL/min/1.73 m ² at baseline: ≥ 50% reduction from baseline	Hold pamiparib until resolved to ≥ 60 mL/min/1.73 m ² 
 • If resolved ≤ 7 days, then maintain dose levels • If resolved > 7 days, then ↓ pamiparib by 1 dose level
Regardless of baseline: < 15 mL/min/1.73 m ²	Permanently discontinue pamiparib

Table 4: Criteria for Modification of Pamiparib Dosing for Related Adverse Events (Continued)

Toxicity	Recommended Dose Modification ^a
Hepatic	
Bilirubin	
Grade 2 (> 1.5 - 3.0 x ULN) Only applies to patients with normal bilirubin at baseline	Hold pamiparib until resolved to ≤ Grade 1 or baseline 
 • If resolved ≤ 7 days, then maintain dose levels • If resolved > 7 days, then ↓ pamiparib by 1 dose level
Grade 3 (> 3.0 - 10.0 x ULN)	Hold pamiparib until resolved to ≤ Grade 1 or baseline 
 • If resolved ≤ 7 days, then maintain dose levels • If resolved > 7 days, then ↓ pamiparib by 1 dose level

Toxicity	Recommended Dose Modification ^a
Grade 4 (> 10.0 x ULN)	Permanently discontinue pamiparib Note: If Grade 3 or 4 hyperbilirubinemia is due to the indirect (unconjugated) component only, and hemolysis as the etiology has been ruled out as per institutional guidelines (eg, review of peripheral blood smear and haptoglobin determination), then ↓ pamiparib by 1 dose level and continue treatment at the discretion of the investigator in discussion with the medical monitor
Aspartate aminotransferase and/or alanine aminotransferase	
Grade 3 (> 5 and ≤ 20 x ULN)	Hold pamiparib until aspartate aminotransferase and/or alanine aminotransferase resolved to ≤ 5 x ULN or baseline 
 • If not resolved within 7 days to ≤ 5 x ULN*, then pamiparib should be decreased by 1 dose level • If second episode, permanently discontinue pamiparib *if other etiologies have been reasonably excluded and not solely based on abnormality/increase of AST/ALT laboratory results
Grade 4 (> 20 x ULN)	Permanently discontinue pamiparib
Pancreatic	
Pancreatitis	
Grade 3 or 4	Permanently discontinue pamiparib
Cardiac	
Cardiac - Prolonged QTc interval	
QTcF > 500 msec or Change in QTc interval > 60 msec from the highest value at baseline or predose	
 • Obtain triplicate electrocardiograms (2 to 3 minutes apart) ~1 hour after initial electrocardiogram • If mean QTcF > 500 ms or mean change in QTc interval > 60 msec, hold pamiparib until evaluation of electrocardiograms by cardiologist 
 ○ Cardiology evaluation as soon as practical but within 7 days of initial abnormal electrocardiogram • If mean QTcF > 500 ms or mean change in QTc interval > 60 msec is confirmed by cardiologist, permanently discontinue pamiparib

**Table 4: Criteria for Modification of Pamiparib Dosing for Related Adverse Events
 (Continued)**

Toxicity	Recommended Dose Modification ^a
Cardiac - General	
Grade 3	Hold pamiparib until resolved to ≤ Grade 1 or baseline and ↓ pamiparib by 1 dose level In the event of acute coronary syndrome, congestive heart failure and myocardial infarction, treatment should be permanently discontinued
Grade 4	Permanently discontinue pamiparib
Other adverse events	
Grade 3	Hold pamiparib until resolved to ≤ Grade 1 or baseline and ↓ pamiparib by 1 dose level No dose reduction required for asymptomatic laboratory abnormalities
Grade 4	Permanently discontinue pamiparib

Abbreviations: CKD-EPI, Chronic Kidney Disease Epidemiology Collaboration; QTcF, QT interval corrected for heart rate using Fridericia’s formula; ULN, upper limit of normal.

^a Dosing of pamiparib can be withheld for up to 28 days consecutively.

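### Table 4's first anemia row pairs a one-level reduction with a fixed 40 mg BID target; the two agree only from 60 mg BID, a minor inconsistency for a patient already at 40 mg BID

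*Protocol*

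**What the plan says.** Protocol Table 3 sets three dose levels: 60, 40 and 20 mg BID. Section 6.1.4 fixes the step size ("Dose reductions are allowed in 20 mg per dose decrements") and the cap ("A maximum of 2 dose reductions is allowed before the patient must be permanently withdrawn from pamiparib").

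The first anemia row of Table 4 applies to any first hemoglobin below 9.0 g/dL. After a hold and recovery to at least 9 g/dL, its instruction is "and then ↓ pamiparib by 1 dose level to 40 mg BID". It mentions neither the current dose nor earlier reductions.

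The later Grade 2 (below 9 to 8 g/dL) and Grade 3 rows open with "Subsequent occurrence following dose reduction for anemia" and offer three options: continue, hold and restart at the reduced level, or hold, "then ↓ pamiparib by 1 additional dose level to 20 mg BID". The Grade 4 row for a second occurrence after an anemia reduction allows only the last of these.

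The action column is headed as a recommendation. On the guidance as a whole, Section 6.1.4 adds: "These general guidelines may be modified at the discretion of the investigator based on discussions with the medical monitor".

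**The concern.** One instruction gives both a relative step and an absolute target, and the two coincide from only one starting point. The non-anemia rows can bring a patient to 40 mg BID before hemoglobin ever falls below 9 g/dL. When it does, the arrow points to 20 mg BID and the printed figure says 40 mg BID.

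A site that followed the printed figure would restart the patient on the dose at which hemoglobin fell. Another site could reduce after the same event. The only analysis this could touch is descriptive: the counts of dose reductions and holds (Protocol 10.5.1; SAP 6.5.1 and 6.5.2), where one event could appear as a reduction at one site and only as a hold at another.

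**Working it through.** **Inputs.** Dose levels 60, 40 and 20 mg BID (Protocol Table 3). Step of 20 mg per dose and a maximum of 2 reductions (Section 6.1.4). Printed target of 40 mg BID (Table 4, first anemia row).

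**The plan's own figure.** From the starting dose, one step is 60 − 20 = 40 mg BID. This reproduces the printed target.

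**The same instruction from each level.**

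| Dose at first Hgb < 9.0 g/dL | By the step | By the printed target | Agree? |
|---|---|---|---|
| 60 mg BID | 60 − 20 = 40 mg BID | 40 mg BID | Yes |
| 40 mg BID | 40 − 20 = 20 mg BID | 40 mg BID (no reduction) | No |
| 20 mg BID | no lower level | 40 mg BID (an increase) | No, but the cap governs |

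At 20 mg BID the patient has used both permitted reductions (60 to 40, 40 to 20), so Section 6.1.4 already deals with that case. The case left open is 40 mg BID.

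**Size of the gap at 40 mg BID.** Step: 2 × 20 = 40 mg/day. Target: 2 × 40 = 80 mg/day. Ratio: 80/40 = 2. Against the starting 2 × 60 = 120 mg/day, these are 40/120 = 33% and 80/120 = 67%.

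**Can a patient be at 40 mg BID before a first Hgb < 9.0 g/dL?** Yes. Grade 3 thrombocytopenia, for example, calls for a hold and then one level down, which takes 60 to 40 mg BID. Table 4 has 12 non-anemia entries that can produce a one-level step: neutropenia 3, thrombocytopenia 2, eGFR 1, bilirubin 3 (including the note on indirect-only elevation), AST/ALT 1, general cardiac Grade 3 1, other Grade 3 1; 3 + 2 + 1 + 3 + 1 + 1 + 1 = 12. None prints a mg target. This counts table entries, not patients.

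**Does another anemia row take over?** No. The later rows, where one step from 40 mg BID does equal the printed 20 mg BID, are conditioned on an earlier reduction for anemia. A reduction for thrombocytopenia does not meet that condition, so the first-occurrence row is the one that applies.

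**What the table allows for a comparable patient.** Take a patient at 40 mg BID after an anemia reduction, with a Grade 2 or 3 recurrence below 9 g/dL. Continuing gives 40 mg BID, hold and restart gives 40 mg BID, and hold and reduce gives 20 mg BID. The permitted set is therefore 40 or 20 mg BID, the same two doses on which the first-occurrence row is ambiguous.

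**The case against.** The best reply is that a sensible reader would not be misled. The instruction is a reduction. A downward arrow that leaves the dose unchanged defeats its own meaning, and Table 3 with the 20 mg decrement rule says what one level is. The printed 40 mg BID then reads as a gloss written with the starting dose in mind. Note 2 in the same anemia block also uses a plain one-level step with no mg figure. This stands: 20 mg BID is the more natural reading.

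Second, there are backstops. The table recommends, and the investigator may depart from it after talking to the medical monitor. Both readings keep the hold until hemoglobin is at least 9 g/dL, and Note 1 requires weekly hematology for Grade 2 or higher anemia until adequate recovery. This also stands, although a discretion clause permits departures from the default without saying what the default is.

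Third, a reader might infer that resuming at 40 mg BID would expose the patient to a dose the protocol treats as unacceptable after such an event. The documents do not support that. The Grade 2 and 3 recurrence rows accept 40 mg BID for a patient at that dose with hemoglobin below 9 g/dL, or even below 8 g/dL, after an anemia reduction.

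The reply does not remove the mismatch. For a reachable patient, the row that applies names a dose that contradicts its own step, and no other row covers that patient.

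**Conclusion.** The inconsistency is real but minor. It is confined to a first hemoglobin below 9.0 g/dL in a patient already at 40 mg BID for a reason other than anemia, where the literal readings differ twofold (40 against 80 mg/day). It rests on reading the later anemia rows as written, that is, only after a reduction for anemia.

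Two stronger conclusions are tempting and unsupported. A reader might infer that sites would have no way of choosing the dose; the arrow, Table 3 and the decrement rule favour 20 mg BID, and the medical monitor can settle a single case. A reader might also infer a frequency from the general anemia experience with the drug. The documents do not give the share of patients who would have a non-anemia reduction first and a first hemoglobin below 9 g/dL afterwards, so no frequency is claimed here.

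The primary and secondary endpoints, the power and the alpha are unaffected. SAP Section 8 reports that the trial stopped after 13 patients were enrolled, so the correction now matters mainly if this dosing table is reused.

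**What to change.** In the Table 4 anemia rows, delete the fixed mg targets (40 mg BID in the first-occurrence row, 20 mg BID in the later Grade 2, 3 and 4 rows). Express each reduction as one dose level, with the ladder in brackets: 60 to 40, or 40 to 20 mg BID. This matches the non-anemia rows, which give the step and no mg target. From 60 mg BID at a first occurrence, and from 40 mg BID at a later one, the resulting dose is the same as now.

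No new rule is needed at 20 mg BID: the existing maximum of 2 reductions covers that patient, and the discretion clause still applies.

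The cost is a few words in one table, with no added visits, procedures or patients and no change to the SAP.

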1.8. Risk-Benefit Assessment

Pamiparib has been studied in nonclinical toxicity and Phase 1 clinical studies. Pamiparib toxicities are largely consistent with the safety profile shared by other PARP inhibitors. The safety profile and adverse drug reactions observed in patients treated with pamiparib monotherapy are summarized in Section 6, Summary of Data and Guidance for the Investigator of the [Pamiparib Investigator's Brochure](#).

MDS and AML have been reported in a small number (< 1%) of patients treated with PARP inhibitors, especially in patients harboring a germline BRCA mutation ([Ricks et al 2015](#)). Typically, patients who develop MDS and AML while on therapy with a PARP inhibitor have a history of extensive previous chemotherapy and some have a history of previous cancer or bone marrow abnormalities. To date, there have been no reports of MDS or AML in patients treated with pamiparib and no fatal adverse drug reactions. Patients in this study will be monitored monthly for hematologic toxicities and events of MDS and AML will be reported as SAEs.

Preliminary data from ongoing monotherapy studies show that pamiparib appears to be generally well tolerated in patients with advanced solid tumors. The safety profile for single-agent pamiparib is similar to those observed in other PARP inhibitors. Some antitumor activity has been observed across the dose ranges evaluated in patients. Therefore, the risk-benefit profile for pamiparib monotherapy is considered acceptable in a patient population with metastatic cancer.

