3. STUDY DESIGN

3.1. Summary of Study Design

This is an open-label, single-arm, global Phase 2 study to evaluate the efficacy and safety of single-agent poly (ADP-ribose) polymerase 1 and 2 (PARP1/2) inhibitor pamiparib in mCRPC patients with CTC-HRD-positive disease or who have a deleterious germline or somatic mutation in BRCA1 or BRCA2.

To be eligible for the study, biomarker-positive patients must have progressed on or after at least one androgen receptor-targeted therapy for mCRPC (eg, enzalutamide, abiraterone acetate/prednisone, bicalutamide, flutamide, apalutamide, or nilutamide), received at least 1 taxane-based therapy for metastatic prostate cancer, and have PSA progression as per PCWG3 criteria at time of study entry. The primary endpoints are ORR by IRC for patients with measurable disease ($n \approx 50$) and PSA response rate for patients with or without measurable disease ($n \approx 80$) as per PCWG3 criteria.

Cohort 1 will include 50 mCRPC patients with CTC-HRD-positive, measurable metastatic disease (soft tissue with/without bone lesions), and positive BRCA1/2 mutation or negative/unknown BRCA1/2 mutation. Cohort 2 will include 30 mCRPC CTC-HRD positive patients with bone metastasis only and positive or negative/unknown BRCA1/2. Cohort 3 and 4 will include 20 mCRPC CTC-HRD negative/unknown patients with BRCA1/2 positive mutations, metastatic disease (measurable soft tissue with/without bone), and bone only (see [Table 2](#)).

After enrollment, patients will receive pamiparib 60 mg orally twice a day in cycles of 28 days.

Safety assessments will occur on Day 1 of each cycle, on Day 15 of Cycles 1 and 2, and as needed. Dose modifications will be made if appropriate ([Section 6.1.4](#)). AEs will be followed and documented during the treatment phase and for approximately 30 days after the last dose of pamiparib or until initiation of new anticancer therapy, whichever occurs first ([Section 9](#) and [Appendix 1](#)). AEs will be graded according to NCI-CTCAE Version 4.03 or higher. A Safety Monitoring Committee will periodically review safety data.

PK samples for pamiparib will be collected at various timepoints at all non-China centers and at centers with such capability in China. In addition, tumor tissue (if available) and blood samples will

be obtained to explore biomarkers of pharmacodynamics, response, and resistance to pamiparib in mCRPC.

[figure not shown]

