Disease status will be assessed by the investigator using PCWG3 criteria ([Appendix 10](#)). Patients will undergo tumor assessments every 8 weeks (± 7 days) for 24 weeks, then every 12 weeks (± 7 days), or as clinically indicated. PSA assessments will occur at screening, on Day 1, and then every 4 weeks (± 7 days), or as clinically indicated.

Administration of pamiparib will continue until PD, unacceptable toxicity, death, or another discontinuation criterion is met ([Sections 5.5.1](#) and [5.6.4](#)). Once the treatment phase has been completed, an End-of-Treatment (EOT) Visit should occur within 7 days of stopping pamiparib with subsequent phases of safety and long-term follow-up.

Long-term follow-up will include tumor and PSA assessments every 12 weeks and 4 weeks (± 7 days), respectively, for those patients without PD, survival status, and initiation of new anticancer therapy. Long-term follow-up will continue until the patient dies or another criterion for discontinuation from study is met ([Section 5.6.4](#)).

Study procedures and assessments are detailed in [Section 7](#) and [Appendix 1](#). The patient cohorts are presented in [Table 2](#) and study schema is presented in [Figure 2](#).

Figure 2: Study Schema

Abbreviations: CTC-HRD+, positive for circulating tumor cells with homologous recombination deficiency per Epic Sciences assay; mCRPC, metastatic castration-resistant prostate cancer; PARPi, PARP inhibitor; PCWG3, Prostate Cancer Clinical Trials Working Group 3; PD, progressive disease; PSA, prostate-specific antigen; RECIST, Response Evaluation Criteria in Solid Tumors.

Notes: Key assessments during the treatment phase: tumor assessments every 8 weeks (\pm 7 days) for 24 weeks, then every 12 weeks (\pm 7 days), or as clinically indicated; and patient-reported outcomes, PSA, adverse events, hematology, and chemistry every 4 weeks. Pamiparib is to be administered continuously.

Table 2: Patient Cohorts

Cohort	1		2		3	4
Patients	n ≈ 50		n ≈ 30		n ≈ 20	
CTC-HRD	+		+		-/∅	
Metastatic disease	Measurable soft tissue ± bone		Bone only		Measurable soft tissue ± bone	Bone only
BRCA1/2 mutation	1A: +	1B: -/∅	2A: +	2B: -/∅	+	

Abbreviations: ∅, biomarker status unknown; CTC-HRD-, negative for circulating tumor cells with homologous recombination deficiency per Epic Sciences assay; CTC-HRD+, positive for circulating tumor cells with homologous recombination deficiency per Epic Sciences assay.

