7.5. Safety Laboratory Assessments

On-study clinical laboratory evaluations starting from screening shall be performed by a central laboratory, as regionally available. An investigator may obtain safety laboratory results from their local laboratory as clinically indicated (eg, on the day of a patient's visit before results are available from the central laboratory for dose modifications or AE/SAE monitoring). Results from the central laboratory will serve as the official study laboratory result, where available. If required by local regulations, clinical laboratory evaluations performed by a local, instead of a central, laboratory are acceptable.

A detailed description of the procedures for sample collection, handling, storage, and shipment of the laboratory samples and all material such as test tubes and labels is provided in the study manual.

Laboratory assessments will be performed at the timepoints specified in [Appendix 1](#) and may also be performed as clinically indicated. Laboratory assessments should be performed before pamiparib

administration. Screening blood tests must be performed within 14 days of Day 1. If tests were performed within 7 days of Day 1, they do not need to be repeated on Day 1.

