Patients who were permanently discontinued from pamiparib for reasons other than PD and meet criteria otherwise (eg, discontinued for AE and no new anticancer therapy) will be followed with tumor and PSA assessments every 12 weeks and 4 weeks (± 7 days), respectively, until PD or any other reason listed in [Section 5.6.4](#), whichever occurs first. For efficacy assessments as per protocol, refer to [Section 7.3](#). If the patient refuses to return for these PSA and tumor assessments or is unable to do so, every effort should be made to contact the patient by telephone to determine the patient's disease status and survival.
Should attempts of telephone contact be unsuccessful, the additional attempts detailed in [Section 5.6.3](#) should be made. If a patient cannot be contacted despite all attempts, the patient will be considered lost to follow-up.
- g. Vital signs (systolic and diastolic blood pressure; pulse rate; and oral, temporal, tympanic, or armpit temperature) will be measured before pamiparib administration and approximately 15 minutes before each collection of PK blood samples, if applicable, during the treatment phase.
- h. ECGs will be obtained approximately every 28 days and at each subsequent visit including EOT. Additional ECGs will be performed, if clinically indicated.
- i. Hematology includes hemoglobin, platelet count, white blood cell count, neutrophil count, and lymphocyte count.
Chemistry includes albumin, alkaline phosphatase, alanine aminotransferase, aspartate aminotransferase, blood urea nitrogen, chloride, creatinine, glucose, lactate dehydrogenase, phosphate, potassium, sodium, total bilirubin, and total protein.
Urinalysis includes blood, glucose, ketones, protein, red blood cells, and white blood cells.
- j. Testing will be performed by a central laboratory and/or the local laboratory at screening and as clinically indicated and will include HBV/HCV serology (hepatitis B surface antigen, hepatitis B surface antibody, hepatitis B core antibody, and HCV antibody) and viral load assessment (HBV DNA and HCV RNA).
- k. PSA levels will be assessed during screening, on Day 1, and every 4 weeks (± 7 days), or as clinically indicated. Responses by PCWG3 criteria must be confirmed ≥ 3 weeks later. Patients without PD at the EOT Visit should be followed with PSA assessments every 4 weeks (± 7 days) during the long-term follow-up phase.

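### Table 4 calls for weekly haematology in Cycles 1 to 3 that Appendix 1 does not schedule, and its renal restart value lies above the baseline of some eligible patients

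*Protocol*

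**What the plan says.** **Haematology.** Note 1 under the anaemia rows of Table 4 (Protocol Section 6.1.4) states: "Weekly hematology test should be done for the first 3 cycles during the study". It does not depend on a low count; weekly testing for Grade 2 or higher anaemia is dealt with in the sentence that follows it. Note 2 asks for a dose reduction to be considered when haemoglobin drops by more than 2 g/dL, "especially within a short time without alternative explanation".

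Section 7.5 governs timing: "Laboratory assessments will be performed at the timepoints specified in" Appendix 1, or as clinically indicated. Appendix 1 marks haematology on Days 1 and 15 of Cycles 1 and 2 and on Day 1 of each later cycle. Its footnote i gives content but no frequency: "Hematology includes hemoglobin, platelet count, white blood cell count, neutrophil count, and lymphocyte count". Section 3.1 agrees with Appendix 1: "Safety assessments will occur on Day 1 of each cycle, on Day 15 of Cycles 1 and 2, and as needed". The Figure 2 notes list "hematology, and chemistry every 4 weeks", and Section 1.8 says "Patients in this study will be monitored monthly for hematologic toxicities".

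**Renal.** Inclusion Criterion 17d admits patients with an eGFR of 30 mL/min/1.73 m² or more. Table 4 has two hold triggers: an eGFR from 15 to below 30 if baseline was at least 60, and a fall of 50% or more if baseline was below 60. There is one release condition for both: "Hold pamiparib until resolved to ≥ 60 mL/min/1.73" m². Recovery within 7 days keeps the dose; later recovery costs one dose level. Below 15, pamiparib stops for good.

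**The concern.** A site that works from Appendix 1, as Section 7.5 tells it to, will not draw weekly counts. Table 4's haemoglobin, neutrophil and platelet actions rest on those counts, and four-weekly counts cannot show whether a haemoglobin drop was fast, which is what Note 2 asks. Blood toxicity is an expected risk here: in the Phase 1 data in Section 1.5.2.3, anaemia was reported in 15 of 45 patients (33%) and related Grade 3 or higher anaemia in 6 of 45 (13%). If some sites follow Note 1 and others follow Appendix 1, the worst post-baseline laboratory grade tabulated under SAP Section 6.5.3 will also reflect how often each patient was tested.

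On the renal side, a patient whose eGFR has returned fully to baseline within a week has not resolved in the sense of Table 4. He stays off drug, loses the option of keeping his dose, and can resume only through a case-by-case exception.

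**Working it through.** The plan gives no figure on this point to reproduce; the check sets its rules against each other.

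**Haematology draws, Cycles 1 to 3** (28-day cycles)

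- Weekly under Note 1: 4 per cycle × 3 = 12, on Days 1, 8, 15, 22, 29, 36, 43, 50, 57, 64, 71 and 78.
- Scheduled in Appendix 1: Days 1, 15, 29, 43 and 57 = 5.
- Unscheduled: 12 − 5 = 7, on Days 8, 22, 36, 50, 64, 71 and 78.
- Longest scheduled gap, in Cycle 3: 85 − 57 = 28 days, against 7 under Note 1. With the ±5-day windows at opposite extremes it is (85 + 5) − (57 − 5) = 38 days.

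**Renal restart against baseline.** For baseline *b* from 30 to below 60, the hold band runs from 15 up to *b*/2, and the restart value relative to baseline is 60/*b*.

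| Baseline eGFR | Hold band | 60/*b* |
|---|---|---|
| 30 | about nil (*b*/2 = 15) | 200% |
| 40 | 15 to 20 | 150% |
| 50 | 15 to 25 | 120% |
| 59 | 15 to 29.5 | 102% |

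The ratio exceeds 100% for every patient to whom this trigger applies.

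**Worked example.** This uses the Appendix 11 equation for a non-black man aged 70 with creatinine 1.5 mg/dL, reading −1.209 as an exponent.

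- Baseline: 141 × (1.5/0.9)^−1.209 × 0.993^70 = 46.5. He meets Inclusion 17d, and his creatinine is below the 2.5 mg/dL limit in Exclusion 14.
- Hold trigger: 46.5/2 ≈ 23.2.
- Inverting, with 141 × 0.993^70 = 86.2: creatinine = 0.9 × (eGFR/86.2)^(−1/1.209). This gives 2.66 mg/dL at eGFR 23.2, 3.82 at 15 and 1.21 at 60.
- He is held from a creatinine of about 2.7 and may restart only at about 1.2 or lower, which is better than the 1.5 he entered with (60/46.5 = 129% of baseline).

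**Comparison with the rest of Table 4.** Nine other hold rows accept return to baseline: neutropenia Grades 3 and 4, thrombocytopenia Grades 3 and 4, bilirubin Grades 2 and 3, AST/ALT Grade 3, cardiac Grade 3 and other Grade 3. The anaemia rows also use a fixed value, 9 g/dL, but that equals the entry floor in Inclusion 17c. The renal value is 60/30 = 2 times its entry floor.

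**The case against.** The strongest reply is that Table 4 is guidance. Note 1 says should, the column is headed as recommendations, and Section 6.1.4 lets the investigator depart from it after talking to the medical monitor. Extra blood counts are allowed under Section 7.5 and at unscheduled visits, and Section 6.1.4 separately asks for weekly counts during prolonged haematologic toxicity. This stands as a limit on the consequence: the protocol does not forbid the draws or omit monitoring. But permission to test when clinically indicated does not schedule a routine test.

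It can also be said that the documents do not show which frequency was intended, since only Note 1 says weekly. The Figure 2 notes list key assessments only, and the monthly wording in Section 1.8 sits in a paragraph on MDS and AML, so neither is strong evidence of conflict. That is fair. The conflict between Note 1 and Appendix 1 does not rest on either.

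On the renal row, Table 4 covers only events judged related to pamiparib, the hold band is narrow at low baselines, and a cautious restart after eGFR has halved might be deliberate. No rationale for that is given, and a separate trigger for baseline below 60 shows that such patients were in view when the row was written.

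Finally, SAP Section 8 records that the trial stopped after 13 patients. That limits the practical effect but does not make the text consistent.

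**Conclusion.** The concern holds on both counts. Seven of the 12 weekly blood counts in Cycles 1 to 3 are missing from the schedule that Section 7.5 makes governing, with none scheduled between Days 57 and 85. Any patient held through the renal trigger for baseline eGFR below 60 must reach 102% to 200% of baseline, across baselines 59 to 30, before the table lets him restart. The renal figures assume that the row is applied as written, without an exception agreed with the medical monitor.

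The haematology gap is the more important of the two because it affects every patient. The documents give no frequency for the renal events, which are probably uncommon. Tumour and PSA follow-up continues after pamiparib stops (Section 5.6.2), so no loss of efficacy follow-up is claimed. Sample size, power and type I error are unaffected. This is a correction that should be made for safety monitoring and dosing.

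**What to change.** 1. In Appendix 1, amend the haematology row or footnote i to read, for example: *Hematology is tested on Days 1, 8, 15 and 22 of Cycles 1 to 3, and on Day 1 of each cycle after that.* Bring Section 3.1, the schema notes, Section 1.8, the matching synopsis text and SAP Section 2 into line. If the sponsor intended the lighter schedule, Note 1 should be narrowed instead, with a reason. Weekly is the better choice given Note 2 and the Phase 1 anaemia rate.
2. In the renal row of Table 4, add *or baseline* after the value of 60 mL/min/1.73 m² in the release condition, and keep the 7-day rule.

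The cost is one footnote, two words and the text alignment, submitted to regulators and ethics committees under Section 11.3.1. The 7 added draws per patient are ones that Note 1 already calls for, and Section 7.5 allows local-laboratory results as clinically indicated. Restarting at baseline means dosing below eGFR 60, but only at the level at which the protocol admitted the patient.
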